Treatment plan: Pinometostat will be given IV starting on day 1 at one of two doses in the phase 1b portion, and at a single defined dose (RP2D) in the phase 2 portion. Pinometostat will continue as a continuous IV infusion through day 35. A bone marrow biopsy will be performed on day 8 to assess the single agent activity. On day 8, standard of care 7+3 with cytarabine and daunorubicin will be initiated. One re-induction attempt is permitted if no CR or CRi is achieved by day 21 (day 14 of 7+3). No further study treatments (e.g. consolidation or maintenance) are planned, and patients should be consolidated as per standard of care.

Phase: 1b, 2

SCHEMA

This study is a multi-site phase 1b/2 study designed to confirm a safe and tolerable dose of pinometostat and to gauge preliminary evidence of efficacy when given as lead-in prior to and contemporaneous with standard intensive induction therapy for newly diagnosed AML with MLL rearrangement. There will be a brief safety run-in phase exploring two dosing schemes, followed by a phase 2 efficacy expansion. The phase 2 expansion will use the higher dose-level of the two schedules if tolerated (see definitions below), otherwise, the lower dose-level if tolerated. The phase 1b/safety run-in portion will have a primary endpoint of Dose-limiting Toxicity (DLT; defined below), while the phase 2 portion will have a primary endpoint of complete remission attainment, and will gather additional laboratory correlative data.

[figure not shown]

Figure 1: Abbreviated Trial Schema (Depicting Initial Induction. Re-induction resets calendar; see details)

Phase 1b/safety run-in phase

The phase 1b portion will operate according to Figure 1. Up to two cohorts will be accrued in order to identify a maximum tolerated dose for expansion. Dose escalation will occur in the standard cohorts-of-3/3+3 design. With only two cohorts (dose levels), escalation stops after cohort 2; if 2-3/3 DLT are observed at dose level 1 (cohort 1), a safety review will be initiated to decide whether dose level reductions below the starting dose should be considered.

Phase 2/expansion phase

The phase 2 portion will use the maximum tolerated dose/schedule and accrue additional patients to gather preliminary evidence of efficacy. Patients will be treated in the same manner as in the phase 1b portion above, with the exception that only a single dose level/cohort will be expanded.

Re-induction

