6.1.3 Re-induction in either Safety Run-in Phase or Expansion Phase

If a patient in either phase (Phase 1b Safety Run-in, or Phase 2 Expansion) requires re-induction due to not achieving a CR/CRi, they will be treated according to the following schedule. Day numbers below refer to a reset calendar where day 1 refers to the first day of re-induction chemotherapy. The study treatment then continues for a total of 28 days.

| Regimen Description | | | | | |
|-------------------------|--|---|--|----------------------|-------------------|
| Agent | Premedications ; Precautions | Dose | Route | Schedule | Cycle Length |
| Pinometostat | Premedications: ondansetron, dexamethasone | 90 mg/m ² /day, unless 60 mg/m²/day has been previously identified as the maximum tolerated dose after completion of the Safety Run-in Phase | Continuous IV infusion | Days 1-28, weeks 1-4 | 28 days (4 weeks) |
| Daunorubicin (as "5+2") | Premedications: ondansetron, dexamethasone | 60 mg/m ² in 50-100 mL NS | IV over 10-30 minutes | Daily, days 1, 2 | |
| Cytarabine (as "5+2") | Premedications: ondansetron, dexamethasone | 100 mg/m ² /day in 1,000 mL NS (per day) | Continuous IV infusion at rate to achieve 100mg/m ² in 24 hours | Days 1-5 | |

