Hematologic DLT will be provisionally defined as an absolute neutrophil count (ANC) < 500/ μ L by day 42 (of first or second induction if applicable) in patients with < 5% blasts in the bone marrow, absence of myelodysplastic changes, and/or absence of evidence of disease by flow cytometry in the bone marrow. Neupogen in this setting may be administered. If persistent cytogenetic abnormalities or immunophenotypic evidence of leukemia is present, myelosuppression would be considered secondary to leukemia even if morphology shows < 5% blasts. Beyond the provisional assignment by day 42, patients who meet above hematologic DLT criteria and continue to have neutrophil < 500/ μ L shall have repeat bone marrow biopsy by day 56. During this additional 2 week period, patients who continue to meet the hematologic DLT criteria shall be DLTs; patients who have evidence of count recovery will not be DLTs.

For patients with > 5% blasts, myelodysplastic changes, or evidence of disease by flow cytometry/cytogenetics, failure to recover neutrophil or platelet count may not be considered DLT as this could be the result of persistent disease.

Also to be considered as DLT: 1) Failure to administer $\geq 75\%$ of planned doses (including in the denominator days needed for re-induction, if any) of the study drug due to therapy related or possibly related non-hematologic toxicities during the defined DLT period. 2) Other related Grade 2 or greater non-hematological toxicities that, in the opinion of the investigator, require a dose reduction or discontinuation of therapy with pinometostat.

All AEs and laboratory toxicities will be graded using the CTCAE version 5.

Management and dose modifications associated with the above adverse events are outlined in Section 6.

Dose escalation will proceed within each cohort according to the following scheme. Dose-limiting toxicity (DLT) is defined above.

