7. DOSING DELAYS/DOSE MODIFICATIONS

No intra-patient adjustment of chemotherapy doses is permitted. No intra-patient escalation of study drug is permitted, except as outlined below and with permission of principal investigator. Dose reduction of pinometostat should occur for grade 3 toxicities possibly related to this agent,

excluding hematologic toxicities and select other toxicities that can occur in the phase 2 expansion portion of the study. These select other toxicities for which a dose adjustment is not required include nausea, vomiting, or diarrhea that is manageable without parenteral or enteral feeding; electrolyte abnormalities that are correctable within 48 hours; and grade 3 infections which are expected in this population.

Daunorubicin and cytarabine are only rarely held during the seven-day intensive induction therapy for AML. Dose modifications to daunorubicin or cytarabine are not recommended for treatment-emergent adverse events, and should be discussed with the principal investigator. For patients with a total bilirubin between 1 and 1.5xULN, the daunorubicin dose may be decreased by 75% after discussion with the principal investigator.

| Event | Management/Next Dose for Pinometostat |
|---------------------|--|
| ≤ Grade 1 | Full dose |
| Grade 2 | Full dose |
| Grade 3 | Hold until recovery of < grade 3, then re-initiate with a one-third dose reduction. For example, if the dose was 90 mg/m ² /day, re-initiate at 60 mg/m ² /day. If the dose was 60 mg/m ² /day, re-initiate at 40 mg/m ² /day. If toxicity reoccurs, therapy should be discontinued. See exceptions in section 6, Dose Limiting Toxicities |
| Grade 4 | Discontinue therapy permanently. |

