10.1.1 CAEPRs for CTEP IND Agent(s)

10.1.1.1 CAEPR for pinometostat

Comprehensive Adverse Events and Potential Risks list (CAEPR) for Pinometostat (EPZ-5676, NSC 795144)

The Comprehensive Adverse Events and Potential Risks list (CAEPR) provides a single list of reported and/or potential adverse events (AE) associated with an agent using a uniform presentation of events by body system. In addition to the comprehensive list, a subset, the Specific Protocol Exceptions to Expedited Reporting (SPEER), appears in a separate column and is identified with bold and italicized text. This subset of AEs (SPEER) is a list of events that are protocol specific exceptions to expedited reporting to NCI (except as noted below). Refer to the 'CTEP, NCI Guidelines: Adverse Event Reporting Requirements' http://ctep.cancer.gov/protocolDevelopment/electronic_applications/docs/aeguidelines.pdf for further clarification. The CAEPR does not provide frequency data; refer to the Investigator's Brochure for this information. Below is the CAEPR for Pinometostat (EPZ-5676).

NOTE: Report AEs on the SPEER **ONLY IF** they exceed the grade noted in parentheses next to the AE in the SPEER. If this CAEPR is part of a combination protocol using multiple investigational agents and has an AE listed on different SPEERs, use the lower of the grades to determine if expedited reporting is required.

| Adverse Events with Possible Relationship to Pinometostat (EPZ-5676) (CTCAE 5.0 Term) | Specific Protocol Exceptions to Expedited Reporting (SPEER) |
|--|---|
| BLOOD AND LYMPHATIC SYSTEM DISORDERS | |
| Anemia | |
| Febrile neutropenia | Febrile neutropenia (Gr 2) |
| Leukocytosis | |
| CARDIAC DISORDERS | |
| Heart failure | |
| GASTROINTESTINAL DISORDERS | |
| Diarrhea | |
| Nausea | |
| Vomiting | |
| GENERAL DISORDERS AND ADMINISTRATION SITE CONDITIONS | |
| Fatigue | |
| INVESTIGATIONS | |
| Alanine aminotransferase increased | |
| Aspartate aminotransferase increased | |
| Blood bilirubin increased | |
| Electrocardiogram QT corrected interval prolonged | |
| Lymphocyte count decreased | |
| Neutrophil count decreased | |
| Platelet count decreased | |
| White blood cell decreased | |
| METABOLISM AND NUTRITION DISORDERS | |
| Hypocalcemia | |
| Hypophosphatemia | |
| SKIN AND SUBCUTANEOUS TISSUE DISORDERS | |
| Rash maculo-papular | |

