10.3.4 Additional Protocol-Specific Expedited Adverse Event Reporting Exclusions

All SAEs, regardless of causality, must be reported to the OSU PI and Multi-Institution Coordinator within 24 hours of knowledge of the event. Initial 24-hour notification using secure email or fax is acceptable. For SAEs not requiring expedited reporting via CTEP-AERS, a complete report accompanied by the SAE Submission Form (refer to Supplemental Forms Document) must be submitted to the OSU PI and Multi-Institution Coordinator via secure email or fax within 5 days of knowledge of the event.

All sites will directly report SAEs requiring expedited reporting to CTEP as outlined in the previous sections.

For this protocol only, the AEs/grades listed below do not require expedited reporting via CTEP-AERS. However, they still must be reported through the routine reporting mechanism (Section 10.4):

| CTCAE SOC | Adverse Event | Grade | ≥24h Hospitalization ^a |
|--------------------------------------|------------------------------------|-------|-----------------------------------|
| Infection | Any | Any | Regardless |
| Blood and lymphatic system disorders | Anemia Bone marrow hypocellular | Any | Regardless |

| CTCAE SOC | Adverse Event | Grade | ≥24h Hospitalization ^a |
|-----------------------------|--|-------|-----------------------------------|
| Investigations | Lymphocyte count decreased Neutrophil count decreased Platelet count decreased White blood cell decreased | Any | Regardless |
| Cardiac disorders | Heart failure | Any | Regardless |
| Gastrointestinal disorders | Mucositis oral | Any | Regardless |
| Renal and urinary disorders | Urine discoloration | Any | Regardless |

^aIndicates that an adverse event required hospitalization for ≥24 hours or prolongation of hospitalization by ≥24 hours of a patient.

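### The Grade 4 row of the Section 7 dose table carries neither the relatedness limit nor the hematologic exclusion given for Grade 3, so read literally it stops pinometostat for a Grade 4 cytopenia

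*Combined protocol and SAP*

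**What the plan says.** Section 7 contains a paragraph and a table that govern pinometostat dosing after toxicity.

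- **Paragraph, relatedness.** "Dose reduction of pinometostat should occur for grade 3 toxicities possibly related to this agent".
- **Paragraph, exclusions.** The same sentence continues: "excluding hematologic toxicities and select other toxicities that can occur in the phase 2 expansion portion of the study".
- **Grade 3 row.** Hold, then restart at a dose one third lower; discontinue if the toxicity recurs. The row points to the exceptions in Section 6.
- **Grade 4 row.** The whole entry is "Discontinue therapy permanently". It has no condition on cause or type of toxicity and no pointer.

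The planned exposure is stated elsewhere. The treatment plan summary says: "Pinometostat will continue as a continuous IV infusion through day 35". Section 6.1.3 says of re-induction: "The study treatment then continues for a total of 28 days".

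Section 6.2 makes an ANC below 500/μL a provisional DLT only at day 42, in a marrow without evidence of leukemia. It confirms the DLT only if the neutropenia persists over the following two weeks, with a repeat marrow by day 56.

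**The concern.** A dosing rule for the study drug should say which events trigger it. The Grade 3 action is limited to possibly related, non-hematologic toxicity. The more drastic Grade 4 action has no limit at all. In a trial that adds pinometostat to 7+3, severe cytopenia is the event most likely to test that gap.

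Two sites could both claim to follow the protocol and dose differently. One stops at the first Grade 4 cytopenia; the other carries the Grade 3 limits across and continues. At the first site the patient loses the rest of the induction infusion. Because the stop is permanent, the patient also loses pinometostat in any re-induction.

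In phase 1b such a patient could also be counted as having tolerated a schedule that was only partly given.

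**Working it through.** The plan gives no figure on this point. The check is a comparison of provisions, followed by an illustration in infusion days.

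**1. Does any other provision supply the missing limits?**

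- Section 7 text: the limits attach to Grade 3 and to dose reduction.
- Section 6.2 exceptions: these define what is not a DLT (fatigue, electrolytes, transaminases, amylase, diarrhea, nausea and vomiting). None exempts a Grade 4 cytopenia from the stopping rule.
- Section 6.5: allows a stop for unacceptable adverse events, with no hematologic carve-out.
- Section 9.1: covers evaluability and attribution, not dosing.
- Section 10: covers reporting.

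No provision supplies them.

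**2. Would a relatedness limit alone be enough?** No. The pinometostat risk list in Section 10.1.1.1 includes decreased neutrophil and platelet counts among events possibly related to the drug. Section 9.1 concedes that attribution is hard in this population. The hematologic exclusion is needed as well.

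**3. Is the literal reading consistent with the rest of the plan?** It fits poorly. Section 10.1.2.2 (daunorubicin) lists cytopenias among the most likely events. Section 6.2 first judges neutropenia at day 42, after the 35-day infusion has ended. Section 3.1.6 sets no minimum ANC or platelet count, so a patient could enter already in Grade 4 cytopenia.

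**4. How would such a stop be counted in phase 1b?** Section 6.2 has a DLT rule for delivering less than 75% of planned doses and another for Grade 2 or higher toxicity that forces a reduction or stop. Both count non-hematologic toxicity only. If counts recover by day 42 or 56, a cytopenia stop is therefore not a DLT. Under Section 9.1 the patient remains DLT-evaluable after one dose and by default is not replaced. One such patient is 1/3 = 33% or 1/6 = 17% of a cohort.

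**5. How much drug would be missed?** Share delivered = infusion days given / infusion days planned. For re-induction, the Section 6.2 convention is "including in the denominator days needed for re-induction, if any". The documents do not give the stop day or the re-induction start day. I assume a stop after study days 12 to 21, and re-induction starting on day 22 (the day after the day 21 marrow) or on day 36 (after a full 35-day infusion).

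| Scenario | Planned days | Delivered |
|---|---|---|
| Induction only | 35 | 12/35 = 34% to 21/35 = 60% |
| Re-induction from day 22, pinometostat barred | 21 + 28 = 49 | 12/49 = 24% to 21/49 = 43% |
| Re-induction from day 36, pinometostat barred | 35 + 28 = 63 | 12/63 = 19% to 21/63 = 33% |

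These shares show what one literal application would cost one patient. They do not estimate how often it would happen.

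**The case against.** The strongest defense is context. The Grade 3 row prints neither limit either; both come from the paragraph that introduces the table. That paragraph can be taken to set the table's subject, naming Grade 3 only because dose reduction is the Grade 3 action. On the literal reading, a patient who entered with a Grade 4 cytopenia would have to stop at once, which cannot have been meant. Section 6.2 also allows growth factor support and attributes cytopenia to leukemia when disease persists. This is a good argument about intent, and I accept that many sites would read the row that way.

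It does not settle the text. A stricter rule at Grade 4 is not absurd: the transaminase and amylase exceptions in Section 6.2 are themselves capped below Grade 4. The exclusion wording is also ambiguous, because its phase 2 qualifier can be read as covering hematologic toxicities too. Phase 1b would then have no hematologic exclusion even at Grade 3.

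Three further points on the other side stand:

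- Falling below 75% delivery through a cytopenia stop triggers nothing in the protocol.
- The 3+3 effect depends on the Section 9.1 evaluability rule, which would equally affect early stops for progression or withdrawal.
- Oversight is close: real-time monitoring by the principal investigator (6.3), recorded stop reasons (6.5), at least monthly calls with CTEP and sign-off on escalation (13.1), and two-weekly site calls with toxicity review for each cohort (13.3). The principal investigator may also add patients at a dose level for safety (9.1).

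A reader might cite Section 10.3.4, which exempts cytopenias of any grade from expedited reporting, as proof that dosing was meant to continue through them. That does not follow. The table concerns reporting only and also exempts heart failure of any grade.

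**Conclusion.** The point holds as a defect in a stated dosing rule. As written, the Grade 4 row would permanently stop pinometostat for marrow suppression that the rest of the plan expects. Two assumptions are needed that the documents do not print: that ANC below 500/μL is CTCAE Grade 4, and that it is expected after 7+3. With an assumed stop on days 12 to 21, the loss for one affected patient would be 40% to 66% of induction infusion days (the complement of 34% to 60% delivered).

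A reader might infer that the protocol contradicts itself outright. It does not: Section 6.2 defines DLTs rather than dosing, and Section 6.5 permits safety stops, so this is an operational inconsistency. A reader might also infer that the 3+3 result or the efficacy analysis is compromised. The documents do not support that. The frequency of literal use is unknown, the surrounding text points the other way, and the reviews in Sections 13.1 and 13.3 would probably reveal such stops, although they do not correct the rule. No alpha, power or sample size figure changes.

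**What to change.** 1. Reword the Grade 4 row: *Grade 4 non-hematologic toxicity at least possibly related to pinometostat: discontinue permanently.*
2. State in the Section 7 text that the hematologic exclusion applies to both the Grade 3 and Grade 4 rows, and in both phase 1b and phase 2. Changing the row alone would leave the Grade 3 rule unclear in phase 1b.
3. Add that persistent neutropenia is assessed under Section 6.2 and that the investigator may still stop for safety under Section 6.5.

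A platelet-based stop or a rule for Grade 4 infection is a clinical choice for the sponsor and is not part of this fix.

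The cost is one table row and a short addition to the text, with no extra data or patients. Section 13.1 already requires an amendment before phase 2. An earlier one is preferable, because the 3+3 count is made in phase 1b.

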8. PHARMACEUTICAL INFORMATION

A list of the adverse events and potential risks associated with the investigational or commercial agents administered in this study can be found in Section 10.1.

8.1 CTEP IND Agent

8.1.1 Pinometostat (NSC #795144)

Chemical Name or Amino Acid Sequence: (2R,3R,4S,5R)-2-(6-amino-9H-purin-9-yl)-5-((((1r,3S)-3-(2-(5-(tert-butyl)-1H-benzo[d]imidazol-2-yl)ethyl)cyclobutyl)(isopropyl amino)methyl)tetrahydrofuran-3,4-diol

Other Names: EPZ-5676, EPZ005676

Classification: DOT1L inhibitor

CAS Registry Number: 1380288-87-8

Molecular Formula: C₃₀H₄₂N₈O₃

M.W.: 562.71 g/mol

Mode of Action: Pinometostat is a selective human DOT1-like, histone H3 methyltransferase (DOT1L) inhibitor. Pinometostat exhibits concentration and time depending inhibition of global methylation of lysine 79 of histone H3 (H3K79) in cultured cells. Pinometostat induces apoptosis in cells that accumulate in the G1/G0 phase. It also inhibits the expression of the key MLL fusion target genes HOXA9 and MEIS1.

Description: A clear to yellow liquid adjusted to a pH of 5.2-6.2 with 1N sodium hydroxide or 1N hydrochloric acid as needed.

How Supplied: Pinometostat is supplied by Epizyme, Inc. and distributed by the Pharmaceutical Management Branch, CTEP/DCTD/NCI. Pinometostat injection is provided as 100 mg/10 mL (10 mg/ml) solution in type 1 borosilicate glass serum single use vials closed with butyl rubber stoppers and aluminum overseals. The other components of the vial include hydroxypropyl betadex, citric acid, anhydrous, sodium hydroxide, hydrochloric acid, and water for injection.

Preparation: Pinometostat must be diluted with 0.9% sodium chloride injection, USP prior to administration to a final concentration between 0.54 mg/ml and 5.63 mg/ml. Add the calculated dose of pinometostat to the appropriate volume of 0.9% sodium chloride in a non-DEHP PVC, polyolefin, or EVA IV infusion bag. **Note: mixing of different drug lots in the same infusion bag should be avoided.** Then gently agitate the infusion bag to ensure mixing. Up to a 90-hour dose may be prepared. An overfill volume of 10% or per institution policy can be prepared to allow for priming of the infusion set tubing. Sites should prepare the appropriate final infusion volume according to standard practice based on a constant flow rate.

Storage: Store intact vials at room temperature between 15 °C -30 °C.

If a storage temperature excursion is identified, promptly return pinometostat to 15 °C -30 °C and quarantine the supplies. Provide a detailed report of the excursion (including documentation of temperature monitoring and duration of the excursion) to [contact] for determination of suitability.

Stability: Stability studies are ongoing. The diluted solution for infusion can be stored for no more than 4 hours at room temperature or for no more than 24 hours stored refrigerated at 2-8 °C prior to infusion. The intravenous infusion is stable at room temperature and can be infused for a maximum of 90 hours. The total time in bag including both preparation and infusion time should not exceed 114 hours. The infusion must be completed within 114 hours after infusion bag preparation.

Route and Method of Administration: Continuous, intravenous infusion via central venous catheter with a pump for up to 90 hours at a constant flow rate. Compatible IV infusion sets are non-DEHP PVC, polyolefin, or EVA with or without a 0.2-micron filter.

Potential Drug Interactions: Pinometostat is metabolized in vitro predominantly by CYP3A with a minor contribution from CYP2C19. It is also a substrate for MATE2-K and likely a weak substrate for OATP1B3, MATE1, and P-gp. Pinometostat is not a substrate for OCT1, OCT2, OATP1B1 or BCRP. Use of strong CYP3A inhibitors and inducers should be avoided. Use caution when administered with strong inhibitors and inducers of CYP2C19, OATP1B3, P-gp, MATE1, and

MATE2-K.

Pinometostat is a weak to moderate inhibitor of CYP3A4/5 in vitro. Pinometostat is an inhibitor of MATE1 and MATE2-K in vitro but not CYP1A2, 2B6, 2C8, 2C9, 2C19, 2D6, P-gp, BCRP, OAT1, OAT3, OCT1, OCT2, OATP1B1, OATP1B3 or BSEP. Use caution with concomitant use of other CYP3A and MATE1 and MATE2-K substrates, especially those with a narrow therapeutic window.

Pinometostat is not an inducer of CYP1A2, 2B6, or 3A4/5 activity or mRNA levels.

Patient Care Implications: Women of child-bearing potential (WOCP) must use acceptable contraceptives while on pinometostat and for 4 weeks after the last dose of pinometostat. Males with partners that are WOCP must use acceptable methods of contraception while on pinometostat and for 90 days after the last dose of pinometostat. It is unknown if pinometostat is excreted in breast milk so should not be administered to nursing mothers.

